### I. Background

Peutz-Jeghers syndrome (PJS) is an autosomal dominant hereditary syndrome, characterized by multiple hamartomatous polyps in gastrointestinal tract, pigmentation in skin mucosa and increased risk of cancer. PJS is a rare disease, with 1 patient in every 8000 to 200,000 births. Large intestinal polyps of PJS patients may lead to local necrosis, hemorrhage, intussusception and intestinal obstruction. The risk of lifelong occurrence of cancer among PJS patients is as high as 64%, with colorectal cancer being the most common one. Average age of cancer diagnosis in PJS patients is 41. At present, there is only invasive treatment for PJS, such as endoscopic polypectomy and surgery, without any drug treatment for choice. Endoscopic polypectomy applies to polyps over 0.5 cm in diameter. However, intestinal segmental resection is required when the polyps are too numerous, or progress into cancer, in which case endoscopic polyps control is infeasible. Invasive treatment exacerbates patients' suffering and increases risk of complications with high medical cost. It may also affect food digestion and absorption, even causing intestinal adhesions and shortbowel syndrome. Therefore, pharmaceutical intervention of PJS' underline pathogenesis is warrented.

The disease is most frequently caused by mutations in LKB1 which is detectable in 50-80% of the PJS family. LKB1 is a tumor suppressor gene. It encodes a serine/threonine kinase which activates the tumor suppressor genes TSC1 and TSC2 via stimulating adenosine 5'-monophosphate-activated protein kinase (AMPK). Activated TSC1-TSC2 complex inhibits the mammalian target of rapamycin (mTOR). Lkb1 deficiency causes PJS through activation of mTOR signaling. Therefore, mTOR inhibitor sirolimus (rapamycin) is a potential therapy for PJS.

Sirolimus is a macrolide antibiotics. It has been used to treat tuberous sclerosis complex, a benign tumor syndrome. The safety of rapamycin is widely recognized. The possible side effects are usually mild and may cause oral ulcers, hyperlipidemia, rash, acne and some other symptoms. While the efficacy of rapamycin on PJS has been demonstrated in mouse model, no clinical trial has been reported.

Cancer susceptibility is a major life-threatening factor of PJS patients. PJSassociated carcinogenesis is related to LKB1-AMPK-mTOR pathway, thus endowing rapamycin with great clinical significance in the treatment or prevention of PJS-related cancer. In 2011, Klümpen et al reported that everolimus, a derivative of sirolimus, was partially effective in the treatment of a PJS patient suffering from advanced pancreatic cancer. No intestinal polyps larger than 1 cm could be found after 8 months' treatment. There have been no evident adverse reactions except for muscle and joint pain of grade 1.

# II. Objectives

- 1. Evaluation of efficacy of sirolimus on Peutz-Jeghers Syndrome.
- 2. Evaluation of safety of sirolimus in treatment of Peutz-Jeghers Syndrome.

# III. Research design

- 1. This study is a prospective, nonrandomized, open-label, single-arm clinical trial. The sirolimus capsule (Rapamycin, Yixinke®), 0.5 mg/grain\*20/box, is produced by North China Pharmaceutical Co., Ltd.
- 2. All patients who meet inclusion criteria and sign informed consents receive sirolimus treatment for at least 6 months. Patients are followed up remotely in a regular schedule.
- 3. No less than 10 patients should be enrolled.

# IV. Selection of subjects

### A. Inclusion criteria

- (1) Patients are diagnosed with PJS.
- (2) Patients have gastrointestinal polyps related syndromes, including abdominal pain, abdominal distension, gastrointestinal bleeding, etc, with imageological

examination suggesting intestinal obstruction or intussusception; or whose symptoms recur after previous digestive system endoscopic treatment and surgery; or who are inappropriate or unwilling to accept the above treatment again and wish to receive pharmacotherapy.

- (3) Conventional treatment doesn't work well in patients with PJS-related malignant tumors.
- (4) Physical condition (ECGO): 0~3
- (5) Organ function is good and biochemical indices meet the following conditions:
  - a) AST <2.5×upper limit of normal value (ULN),
  - b) ALT <2.5×upper limit of normal value (ULN),
  - c) Serum total bilirubin (TSB)≤1.5×upper limit of normal value (ULN),
  - d) Creatinine <1.5×upper limit of normal value (ULN).
- (6) No other medications have been received for intestinal polyps within 3 months prior to the clinical trial.
- (7) Patients volunteer to participate in the trial. Participant or his/her legal guardian signs the informed consent form.

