### D. Rejection criteria

- (1) Patients who violate the requirements of the test protocol
- (2) Patients with poor-recording, incomplete, or inaccurate data

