### VI. Follow-up plan and content

#### A. Evaluation before the trial

Each subject should complete the following items in four weeks before the treatment:

1) Complete medical history

2) Detailed personal profile

3) A physical examination

4) VAS pain score

5) (Patients suspected with secondary malignant lesions) tumor markers examination, including CEA, CA199 and CA125

6) (Female aged 25 or elder) ultrasonic examination of uterus and its appendages

7) Blood and urine routine examination

8) Liver and kidney function, blood lipid test

9) (Patients with secondary malignant tumor) chest CT and other related examinations

10) Abdominal and pelvic cavity contrast-enhanced CT + small intestine reconstruction CT examination

11) Digestive system endoscopy

12) (Female of childbearing age) blood/urine pregnancy test

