### B. Evaluation during sirolimus treatment

Adverse reactions are evaluated weekly during the first month of drug treatment. The efficacy and safety are then evaluated at the 3rd and 6th months, and the contents of the examination is the same as the pre-trial evaluation.

1) Efficacy assessment:

a. Clinical symptom assessment (including ileus, VAS pain score, gastrointestinal bleeding and some other related symptoms);

b. Changes in hemoglobin;

c. Nutritional status (including albumin, etc.);

d. Abdominal and pelvic cavity contrast-enhanced CT + small intestine reconstruction CT examination, digestive system endoscopy to measure the size, quantity and total load of intestinal polyps;

e. (For patients with secondary malignant tumor) Tumor response to the drug, such as changes of tumor marker, tumor regression shown by imaging, metastasis and etc.

2) Safety assessment: Safety parameters (such as asking adverse events, measuring laboratory values, vital signs, gastrointestinal bleeding, etc.) will be closely monitored on a regular basis throughout the study.

3) Treatment compliance: In order to monitor compliance, subjects are required to complete an electronic diary during the entire study period. Dates of drug intake will be tracked by this diary. At every visit, the investigator and the subject will review the integrity of the electronic diary data together.

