#### **C.** Evaluation after treatment

Evaluation of curative effects and safety is conducted at the end of the drug therapy, six and twelve months after the treatment. Its content is the same as pre-trial evaluation.

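### A treated patient who misses a required endoscopy can be rejected for incomplete data although CT polyp measurements exist, and no analysis set or missing-data rule prevents it

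*Combined protocol and SAP*

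**What the plan says.** Inclusion criterion (2) in IV.A has alternatives joined by *or*. One is patients "whose symptoms recur after previous digestive system endoscopic treatment and surgery". The next is patients "who are inappropriate or unwilling to accept the above treatment again and wish to receive pharmacotherapy". The treatment meant is therefore the endoscopic treatment and surgery named just before. The Background describes such treatment as therapy: "there is only invasive treatment for PJS, such as endoscopic polypectomy and surgery".

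Section VI.A opens with "Each subject should complete the following items in four weeks before the treatment". Item 10 is CT with small-intestine reconstruction and item 11 is "Digestive system endoscopy". Items 5, 6, 9 and 12 carry a condition in brackets; items 10 and 11 do not. VI.B repeats the baseline content at months 3 and 6. VI.C adds the end of therapy and 6 and 12 months afterwards, and states: "Its content is the same as pre-trial evaluation".

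For efficacy, VI.B item 1d names the CT together with "digestive system endoscopy to measure the size, quantity and total load of intestinal polyps". The rejection criteria in IV.D include, as item 2, "Patients with poor-recording, incomplete, or inaccurate data". Section VIII.B(2) says that polyp size, volume and total load will be analysed. It does not say in which patients, or what happens when a measurement is missing.

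**The concern.** A repeated invasive examination is compulsory, and incomplete data are a ground for rejection. Nothing says how much must be missing, or that a patient with the other polyp measurement is kept. The investigators could therefore decide who counts after seeing how each patient did. In a single-arm trial with a floor of 10 patients, every exclusion changes the denominator visibly, and no control arm would show a distortion.

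The entry criteria sharpen the question. One route selects patients who are unsuited to a repeat of endoscopic treatment or surgery, or who refuse it. It is reasonable to ask whether they would miss more study endoscopies than others. If they did, and were rejected for it, the polyp result would under-represent a group that the protocol names as eligible.

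**Working it through.** The plan states no power, effect size or sample-size calculation, so it offers no figure to reproduce. The check has two parts.

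**Tracing the text**

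1. Endoscopies per patient: baseline, month 3, month 6, end of therapy, and 6 and 12 months after treatment, which makes 6. If therapy ends at month 6, two of these coincide and there are 5. The weekly checks in month 1 cover adverse reactions only and do not count.
2. Exemptions from endoscopy: none found.
3. Other source of polyp data: CT, at the same evaluations.
4. Rule for polyp load when one source is missing: none found.
5. Meaning of *incomplete* in IV.D(2): not given. Rejection is listed apart from the exit criteria in IV.C, so removal from the analysis is a natural reading, but it is not stated.
6. Analysis set or missing-data rule in VIII: none found.

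A missed endoscopy can therefore lead to rejection, although the text does not say that it must.

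**What rejection could cost (all rates assumed)**

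If each endoscopy is accepted independently with probability p, a complete set of k has probability p^k:

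| p | k = 2 (baseline and month 6) | k = 5 | k = 6 |
|---|---|---|---|
| 0.95 | 90% | 77% | 74% |
| 0.90 | 81% | 59% | 53% |
| 0.80 | 64% | 33% | 26% |

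The k = 5 and k = 6 columns apply only if one missing examination makes a patient incomplete. The k = 2 column is what a baseline-to-month-6 endoscopic comparison needs. The gap between them shows how much depends on an undefined word. The table uses one common rate and says nothing about differences between entry routes.

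*Precision.* The half-width of a 95% t-interval for a mean is t × SD / √n. With 7 patients in place of 10 and the same SD, the ratio is (2.447/√7) / (2.262/√10) = 0.925/0.715 = 1.29, about 29% wider.

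*Bias.* Suppose 3 of 10 are rejected, their mean change is 0% and that of the other 7 is −30%. The mean over all 10 is 0.7 × (−30) + 0.3 × 0 = −21%, but −30% would be reported. If both groups change equally, the bias is zero.

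*Bounds.* Take an assumed yes/no polyp response, with m of 10 patients rejected and x responders among those kept. The rate in all 10 then lies between x/10 and (x + m)/10:

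| m | Observed | Exact 95% interval | Possible rate in all 10 |
|---|---|---|---|
| 0 | 5/10 | 18.7–81.3% | 50% |
| 2 | 4/8 | 15.7–84.3% | 40–60% |
| 3 | 3/7 | 9.9–81.6% | 30–60% |
| 4 | 3/6 | 11.8–88.2% | 30–70% |

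Each rejected patient adds 10 percentage points to the possible range.

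**The case against.** A reader might infer that the protocol contradicts itself: it recruits patients who cannot or will not have endoscopy, then demands it, so that this group's polyp results are lost selectively. The documents do not support that, for four reasons.

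- **Treatment is not measurement.** The entry route concerns repeat endoscopic treatment and surgery. The Background's example of endoscopic therapy is polypectomy. The evaluations require endoscopy as an examination. Some of these patients may object mainly to more surgery. No passage says that they refuse, or cannot have, a diagnostic endoscopy. This stands.
- **Baseline endoscopy filters entrants.** Someone who would not have it would not complete the work-up in VI.A. This stands in part. Completing the work-up is not an inclusion criterion, and section III says that all who meet the criteria and consent are treated. Accepting one endoscopy also does not commit a patient to four or five more.
- **CT measures polyps at the same visits.** A missed endoscopy does not erase the polyp data. This stands, and it is why rejecting such a patient would be wasteful. But the plan does not say that CT alone suffices, or how to compare a CT-only visit with one that had both.
- **IV.D(2) may never be applied this way.** That is possible, because its scope is undefined. The lack of definition is itself the defect.

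Nor does any passage suggest that response to sirolimus differs by entry route. Without a difference in response between those kept and those rejected, loss costs precision only.

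**Conclusion.** The weakness lies in the combination of compulsory endoscopy at 5 or 6 evaluations, an undefined rejection rule for incomplete data, and no analysis set or missing-data rule. Together they allow a treated patient with usable CT polyp data to be rejected. This applies to every patient, whatever the entry route. More missed endoscopies among those entering because they are unsuited to, or unwilling to repeat, earlier treatment is a plausible inference and no more. The documents give neither the size of that group nor any rate of missed examinations, and the loss could be zero.

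The possible size rests on assumptions. With 3 of 10 rejected, the interval for mean change is about 29% wider. The mean is overstated by 9 percentage points only under the assumed contrast of 0% against −30%. The point deserves correction before analysis because the number of patients may be as low as 10 and the remedy needs no new examination.

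**What to change.** - **IV.D(2):** state that a missing endoscopy, or any other single missing assessment, does not remove a treated patient from the analysis. Say the same for item (1), so that a declined endoscopy does not lead to rejection as a protocol violation instead.
- **VIII.B(2):** analyse efficacy in all treated patients. Use the CT polyp measurements for those without endoscopy. Within a patient, compare like with like: CT with CT, endoscopy with endoscopy.
- **Reporting:** give the number of missing endoscopies at each evaluation and every exclusion with its reason, listed by entry route. With about 10 patients this should be a listing, not a subgroup analysis.
- **Schedule:** leave endoscopy as planned. Making it optional would invite self-selection in that measure.

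The cost is a few sentences of protocol text and slightly more reporting. The drawback is that CT may miss small polyps, so the result is less sensitive in patients without endoscopy. If a whole visit is missed, CT is missing too; the patient still stays in the denominator and the gap is reported.

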### **B.** Exclusion criteria

- (1) Patients underwent a surgery within 2 weeks.
- (2) Patients may need emergency surgery in the near future.
- (3) Patients are allergic to any ingredient of rapamycin.
- (4) Patients suffer from a disease requiring immediate blood transfusion.
- (5) Patients suffer from any disease or condition that may impact implementation of the study or interpretation of the results. This type of diseases includes:
  - a) Known severe blood coagulation disorders
  - b) Known anemia that is not caused by intestinal polyps
  - c) Known hemoglobinopathy
  - d) Other gastrointestinal infectious diseases
  - e) Serious heart, liver, kidney and other concomitant diseases that may endanger lives
- (6) Patients are in pregnancy and lactation.
- (7) Alcohol or drug (such as aperient) abuse
- (8) Patients took part in another clinical trial that may influence this study.
- (9) The researchers believe that there are other unfavorable reasons for the patient to become a subject.

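### The pre-treatment windows allow the baseline to predate a polyp removal, and in this single-arm trial that removal would be counted as a fall in polyp load under sirolimus

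*Combined protocol and SAP*

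**What the plan says.** Timing of baseline (Section VI.A): "Each subject should complete the following items in four weeks before the treatment". The items include abdominal and pelvic CT with small-bowel reconstruction, "Digestive system endoscopy", the VAS pain score, routine blood tests, and liver and kidney function. Nothing orders these items relative to a procedure, and nothing says whether polyps may be removed at the endoscopy.

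Bars on earlier treatment:
- Exclusion (1), Section IV.B: "Patients underwent a surgery within 2 weeks". No reference date is given (screening, baseline or first dose).
- Exclusion (2), Section IV.B: "Patients may need emergency surgery in the near future". This concerns emergency surgery only.
- Inclusion (6), Section IV.A: "No other medications have been received for intestinal polyps within 3 months prior to the clinical trial". This concerns drugs only.

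The protocol treats polypectomy and surgery as two different things. Section I describes invasive treatment "such as endoscopic polypectomy and surgery, without any drug treatment for choice", and adds "Endoscopic polypectomy applies to polyps over 0.5 cm in diameter". One branch of Inclusion (2) admits patients "or whose symptoms recur after previous digestive system endoscopic treatment and surgery", with no minimum interval since that treatment.

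Section VI.B takes efficacy from symptoms including VAS pain, hemoglobin, albumin, and the size, number and overall burden of polyps on CT and endoscopy. Section III describes one open-label arm of at least 10 patients. Section VIII plans descriptive summaries and makes no allowance for recent polyp removal.

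**The concern.** With no control arm, every efficacy statement is a comparison with the patient's own baseline. That comparison needs the baseline to describe the patient as he or she was when treatment began. The windows do not secure this, in two distinct ways.

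1. **Baseline before removal.** If polyps are counted and then taken out before the first dose, the month 3 and month 6 load is lower even if sirolimus does nothing. This affects the polyp outcomes.
2. **Baseline soon after a procedure.** Hemoglobin, albumin and pain may be temporarily poor and improve as the patient recovers. This affects those outcomes and not polyp load.

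Both arise before the first dose, so a rule for handling removals during treatment would not deal with them.

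**Working it through.** The plan gives no figure of its own to reproduce. The check is whether the stated windows permit the two situations, and then how large the first could be.

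**Step 1: timing.** Let day 0 be the first dose. The baseline day B runs from -28 to -1 (Section VI.A). The procedure day S was taken from -56 to -1. Whole-day pairs (B, S) that pass the timing criteria were counted. Baseline before removal means S later than B. Baseline soon after means 0 to 14 days from S to B.

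| Procedure and reading of the bar | Baseline before removal | Baseline 0 to 14 days after |
|---|---|---|
| Surgery, two weeks counted back from first dose | 91 | 315 |
| Surgery, two weeks counted back from baseline or screening | 378 | 0 |
| Endoscopic polypectomy, no bar | 378 | 420 |

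How the counts arise:
- Counted from first dose, surgery is allowed up to day -15. Baselines on days -28 to -16 can precede it, giving 13 + 12 + ... + 1 = 91.
- Counted from baseline, or with no bar, any later pre-dose day is open, giving 27 + 26 + ... + 1 = 378.
- For polypectomy soon before baseline: 28 baseline days x 15 gaps = 420.
- For surgery counted from first dose: 14 x 15 = 210 for baselines on days -28 to -15, plus 14 + 13 + ... + 1 = 105 for later baselines, total 315.

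These counts show what is permitted. They are not probabilities. Baseline before removal is possible under either reading of Exclusion (1). A baseline soon after surgery needs the first-dose reading; a baseline soon after polypectomy is possible under either.

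**Step 2: size of the polyp-load effect.** Assume no drug effect and 10 patients (the minimum in Section III), of whom k lose a fraction f of their load between baseline and first dose. Then

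spurious mean change = -(k/10) x f.

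| k | f = 30% | f = 50% | f = 70% |
|---|---|---|---|
| 1 | -3% | -5% | -7% |
| 2 | -6% | -10% | -14% |
| 3 | -9% | -15% | -21% |

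Both k and f are assumptions; the documents give neither. In every cell at least 7 of the 10 patients have zero change, so the 5th and 6th ordered values are both 0 and the median change is 0. The affected patients appear as the minimum.

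**Step 3: direction.** Removal after baseline exaggerates the fall in polyp load. Removal before baseline lowers the starting load, which does not favor sirolimus on that outcome, while it leaves hemoglobin, albumin and VAS open to improvement through recovery.

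**The case against.** Several points on the other side carry weight.

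- **The surgical path is uncommon.** Consent comes before screening (Section V.A), so a patient with a baseline CT has ordinarily already agreed to drug treatment. Inclusion (2) looks for obstruction or intussusception on imaging, recurrence after earlier treatment, or unsuitability or unwillingness for more procedures. An elective resection a week after baseline could remove the reason for entry. This stands, and makes that sequence an edge case. It does not close the gap, since no timing rule forbids it.
- **Discretion.** Exclusions (5) and (9) let investigators turn away unsuitable patients. But (5) concerns diseases and conditions, its examples include no recent procedure, and neither item fixes when baseline is taken.
- **Removal at the baseline endoscopy is not stated.** Section VI.B describes endoscopy as a means of measurement. That is correct; the plan is silent on removal rather than providing for it.
- **Descriptive analysis.** Section VIII.A also calls for the median, quartiles, minimum and maximum, so the summary would not rest on the mean alone. This limits the harm.
- **Different purposes.** The three-month interval for drugs deals with carry-over, so it is not a benchmark for procedures. Accepted; no weight is put on that contrast.

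A reader might infer that the windows tilt every efficacy outcome toward sirolimus. They do not: the two mechanisms act on different outcomes, and a load measured after removal works the other way. A reader might also infer that Exclusion (1) must be lengthened to four weeks. The documents do not support that. Counted to first dose, four weeks would still allow a day -29 operation followed by day -28 blood tests and VAS, and it would exclude anyone with polyps removed at the baseline endoscopy itself.

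**Conclusion.** The point holds as a gap in ordering. Under either reading of Exclusion (1), the sole comparator for polyp load can predate a surgical or endoscopic removal, and nothing in the analysis would separate that from a sirolimus effect. The recovery problem for hemoglobin, albumin and VAS is a second, separate gap.

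The documents establish that this can happen, not that it will or how often. The range of -3% to -21% in the mean rests wholly on the assumed 1 to 3 of 10 patients and 30% to 70% of load removed, with the median at 0 throughout. With as few as 10 patients, one or two cases are enough to move the mean, and the remedy is small, so it should be made.

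**What to change.** 1. **Section VI.A, ordering rule.** Require that the baseline CT, endoscopy, hemoglobin, albumin and VAS used for efficacy postdate the last surgery or endoscopic polypectomy, and that no such procedure falls between them and first dose. If one does, repeat the affected baseline measures before first dose.
2. **One exception.** Polyps removed at the Section VI.A endoscopy itself are taken out of the baseline count using the endoscopy report.
3. **Exclusion (1).** State the date from which the two weeks are counted. The sponsor should reconcile this criterion with the four-week baseline window and say whether it covers endoscopic polypectomy. The length of the interval is for the sponsor and is not prescribed here.
4. **Section VIII.** Record the date of the last procedure for each patient. In a sensitivity summary, flag patients whose baseline hemoglobin, albumin and VAS were taken soon after it. This is needed because the ordering rule alone does not remove the recovery problem.

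Cost: a short wording change, one extra recorded date and one additional summary. The downside is an occasional repeat baseline examination, or a short delay to first dose, for patients with a recent procedure.
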